5.7 Statistical Tests

No hypothesis tests are planned for this study; therefore p-values will not be provided. For estimation purposes, two-sided 95% confidence interval (CI) will be supplied for secondary efficacy endpoints and EAIRs.

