6.2.1 Multiple Imputation

For the vIGA-AD secondary efficacy endpoints (refer to Section 12.2), vIGA-AD non-imputed values collected during the parent studies and this study (including the last available data of subjects who prematurely withdraws from this study) will be appended together after having been assigned to pre-specified analysis visit using the analysis windows defined in their respective study (parent study SAPs or this SAP Section 5.4, as applicable). Doing so, each subject will have between 4 (subjects who enrolled in OLE and discontinued early before the first application of

 Innovaderm Research	STATISTICAL ANALYSIS PLAN, Final Version 1.0
Protocol Number: ARQ-151-313	Sponsor: Arcutis Biotherapeutics, Inc.

roflumilast cream during the OLE study) to 7 (subjects in Cohort-Week 24 who completed the OLE) or 9 (subjects in Cohort-Week 52 who completed the OLE) vIGA-AD non-imputed values:

OLE Analysis Visit	Study/Analysis Visit
OLE Week -4	Parent study derived baseline value (refer to parent study Section 5.2)
OLE Week -3	Parent study / analysis visit Week 1
OLE Week -2	Parent study / analysis visit Week 2
OLE Day 1	Parent Study / analysis visit Week 4
OLE Week 4	OLE study / analysis visit Week 4
OLE Week 12	OLE study / analysis visit Week 12
OLE Week 24	OLE study / analysis visit Week 24
OLE Week 36*	OLE study / analysis visit Week 36
OLE Week 52*	OLE study / analysis visit Week 52

* Cohort-Week 52 subjects only.

Note: No missing data are expected for the OLE Week -4 to OLE Day 1 analysis visits since subjects must have completed a parent study to be eligible for enrollment in this OLE study.

Then, to comply with the definition of the parent studies' primary estimand (refer to parent studies Section 12.1.1), efficacy data assigned to a pre-specified analysis visit will be removed from the source data used for the multiple imputation process if subject's last dose day falls within the analysis visit window or is prior to the start of the analysis visit window used to assign data to a pre-specified analysis visit (refer to Section 12.2) for subjects who discontinued due to lack of efficacy or adverse event. This procedure will ensure that the data collected on or after intercurrent events are not used in the imputation process.

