vIGA-AD missing values will be imputed before deriving the vIGA-AD secondary efficacy endpoints (refer to Section 12.2), using a Predictive Mean Matching (PMM) sequential-regression multiple imputation model for the Full Analysis Set population as per the following three-step process.

1. The first step is to understand the pattern of missingness. In order to perform the multiple imputation, a monotone missing pattern has to be achieved. For example, if there exist values for OLE Week 4 and OLE Week 24 visits, but missing values for the OLE 12 visit, the Markov-Chain Monte-Carlo (MCMC) method will be used to impute the small amount of missing data that may be missing at the intermediate visits that is required to make the missing data pattern monotone before applying the multiple imputation algorithm. This

 Innovaderm Research	STATISTICAL ANALYSIS PLAN, Final Version 1.0
Protocol Number: ARQ-151-313	Sponsor: Arcutis Biotherapeutics, Inc.

method uses a non-informative Jeffreys prior to derive the posterior mode from the expectation-maximization (EM) algorithm as the starting values for the MCMC method. The MCMC method will use the seed 6457149. The model will include the parent study randomized vIGA-AD stratification variable and parent study randomized treatment group (refer to Section 5.5), both as categorical variables, as well as all vIGA-AD scores collected at scheduled visits during both the parent and OLE studies, all as continuous variables. To avoid values that could not be observed in practice, imputed values will be rounded to the nearest integer (Round=1 option in PROC MI) in the range of 0 to 4.

To determine the number of multiply imputed datasets to be created at this step, the proportion of datapoints with non-monotone pattern across all visits and subjects will first be derived as follows:

$$\frac{\text{number of non monotone visits accross all visits and subjects}}{\text{total number of expected visits accross all subjects}} * 100$$

Of note, the total number of expected visits across all subjects is not the same for the Cohort-Week 24 subjects and Cohort-Week 52 subjects i.e., 7 visits during the OLE study for Cohort-Week 24 subjects and 9 visits during the OLE study for the Cohort-Week 52 subjects.

Then, the following table will be used:

Non-monotone Missing Data	Number of Imputed Datasets
$\leq 2\%$	1
$> 2\% \text{ to } \leq 5\%$	3
$> 5\%$	10

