- Once the monotone pattern is achieved, the next step is to implement the imputation algorithm. For this, the PMM regression method will be used. This method is particularly helpful if the normality assumption is violated. For subjects with complete data up to a particular visit, a PMM regression model will be fit that includes the outcome at that visit as the dependent variable and as independent variables, the parent study randomized vIGA-AD stratification variable and parent study randomized treatment group, both as categorical variables, as well as the vIGA-AD score outcomes at previous analysis visits, all as continuous variables, using a seed of 482371. This process will be repeated 25 times, resulting in a total of 25 to 250 complete analysis datasets, depending on the number of

 Innovaderm Research	STATISTICAL ANALYSIS PLAN, Final Version 1.0
Protocol Number: ARQ-151-313	Sponsor: Arcutis Biotherapeutics, Inc.

imputed monotone datasets that are required. The seed may be changed after unblinding in case of any issues with the imputation process, and it will be documented in the CSR if any change is required.

3. For each multiply imputed dataset, Primary or OLE Baseline values, as applicable, will be derived as defined Section 5.2 and analysis visits from parent studies (OLE Week -4 to OLE Day 1) not selected as Primary or OLE Baseline, as applicable, will be dropped from each multiple imputed dataset.

For Cohort-Week 24 subjects, imputed OLE Week 36 and Week 52 analysis visit values will be set to missing given that these subjects will complete study at Week 24 or discontinue early from study before Week 24, whichever occurs first.

Finally, for each completed dataset, the vIGA-AD secondary efficacy endpoints will be derived by visit, as described in Section 12.2. Common proportion of success/achievement (and associated standard error [SE]) will then be calculated overall and by treatment group for each OLE analysis visit and combined using PROC MIANALYZE based on Rubin's rule to obtain a combined common proportion of success/achievement for each OLE analysis visit overall and treatment group. The combined common two-sided 95% CI will be calculated as per Lott and Reiter (2020)¹ multiple imputation Wilson interval method

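### When at most 2% of expected visits are non-monotone, SAP 6.2.1 singly imputes the intermittent vIGA-AD gaps, so the visit-level 95% CIs come out slightly too narrow

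*SAP*

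**What the plan says.** SAP 6.2.1 (Multiple Imputation) covers the two vIGA-AD secondary endpoints.

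- **Step 1.** MCMC makes the missing-data pattern monotone. It "will be used to impute the small amount of missing data that may be missing at the intermediate visits".
- **Number of step 1 datasets.** For this, "the proportion of datapoints with non-monotone pattern across all visits and subjects will first be derived". A table then gives 1 dataset for a share of at most 2%, 3 datasets for more than 2% up to 5%, and 10 above 5%.
- **Denominator of that share.** It counts "7 visits during the OLE study for Cohort-Week 24 subjects and 9 visits during the OLE study for the Cohort-Week 52 subjects". The visit table earlier in 6.2.1 shows that four of these (OLE Week -4, Week -3, Week -2 and Day 1) come from the parent study, and the note beneath it states: "No missing data are expected for the OLE Week -4 to OLE Day 1 analysis visits".
- **Step 2.** PMM fills what is still missing in each monotone dataset: "This process will be repeated 25 times, resulting in a total of 25 to 250 complete analysis datasets".
- **Pooling.** The visit proportions are "combined using PROC MIANALYZE based on Rubin's rule", and the interval is the multiple-imputation Wilson interval.

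SAP 5.7 plans no hypothesis tests; for estimation, "two-sided 95% confidence interval (CI) will be supplied for secondary efficacy endpoints and EAIRs". SAP 12.2.1 makes this the main analysis of the vIGA-AD endpoints, and 12.2.3 repeats it in subgroups.

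**The concern.** Rubin's rule measures imputation uncertainty by how much results differ between completed datasets. With one step 1 dataset, each intermittent gap is drawn once and that draw is carried into all 25 completed sets. PMM varies only the values after dropout. The gaps therefore contribute no between-imputation variance of their own, and the pooled interval treats them almost as if they had been observed.

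With 3 or 10 step 1 datasets, the 75 or 250 completed sets come in groups of 25 that share the same intermittent values. The SAP pools them by the ordinary rule and gives no combining rule for nested sets.

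The choice of branch rests on a percentage that includes visits at which no gaps are expected. It is also pooled over all subjects and visits, so gaps concentrated at one visit or in one subgroup do not change the branch. At stake is the width of the 95% CIs for visit-level vIGA-AD proportions. With no tests planned, these are the only statement of precision for those endpoints.

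**Working it through.** **The plan's own figure.** Datasets = step 1 datasets × 25: 1 × 25 = 25, 3 × 25 = 75, 10 × 25 = 250. This reproduces the stated range and confirms that its lower end is the one-dataset branch.

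**What 2% means on OLE visits.** Removing the four parent visits leaves 7 - 4 = 3 (Cohort-Week 24) or 9 - 4 = 5 (Cohort-Week 52). Assume 1500 subjects: 550 in Cohort-Week 24 (275 + 275, from the protocol's Summary of Changes) and the other 950 in Cohort-Week 52.

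- Expected visits: 550 × 7 + 950 × 9 = 12,400; 2% of these is 248 gaps.
- OLE visits: 550 × 3 + 950 × 5 = 6,400; 248/6,400 = 3.9%.
- If all subjects were in one cohort: 2% × 9/5 = 3.6% or 2% × 7/3 = 4.7%.
- A missed last visit is not intermittent. Over the remaining 550 × 2 + 950 × 4 = 4,900 visits the share is 5.1%.
- All gaps at one visit: 248/1500 = 16.5% of subjects.

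**Effect on the interval.** Let f be the share missing at a visit, completely at random, and R² the share of variance predicted by other visits (assumed 0 to 0.5). Dropout is ignored.

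- Complete-data variance W = p(1 - p)/n; between-imputation variance B = W·f(1 - R²)/(1 - f).
- One step 1 dataset: reported variance W; true variance W + 2B.
- 25 independent draws: reported variance W + (1 + 1/25)B.
- Width of the first relative to the second: 1/√(1 + 1.04·B/W). Coverage of the first: 2Φ(1.96/√(1 + 2B/W)) - 1.

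Worked example, f = 3.875%, R² = 0: B/W = 0.03875/0.96125 = 0.0403; width ratio 1/√1.0419 = 0.980; coverage 94.1%.

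| f | CI narrower by (R² 0.5 to 0) | Coverage (R² 0.5 to 0) |
|---|---|---|
| 3.6% | 1.0 to 1.9% | 94.6 to 94.1% |
| 3.9% | 1.0 to 2.0% | 94.5 to 94.1% |
| 4.7% | 1.3 to 2.5% | 94.4 to 93.9% |
| 5.1% | 1.4 to 2.7% | 94.4 to 93.8% |
| 16.5% (one visit) | 4.8 to 8.9% | 92.7 to 90.3% |

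At p = 0.5, n = 1500 and R² = 0, the half-width is 2.53 percentage points in the one-dataset branch. With 25 independent draws it is 2.58 at f = 3.9% and 2.78 at 16.5%.

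**Nested branches.** Ordinary pooling of k × 25 sets captures 25(k - 1)/(25k - 1) of B, while the true variance is W + (1 + 1/k)B. At f = 3.6% and R² = 0 (B/W = 0.0373):

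- k = 3: √(1.0256/1.0498) = 0.988, a shortfall of 1.2%.
- k = 10: √(1.0339/1.0411) = 0.9965, a shortfall of about 0.35%.

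These are relative to the estimator's own true SE. On that scale the one-dataset branch falls short by 1 - 1/√1.0747 = 3.5%.

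**Simulation checks.** With latent normal scores, n = 500, correlations of 0 to 0.7 and 4,000 runs, one draw against 25 gave intervals 1.4 to 2.1% narrower at f = 4% (coverage 93.9 to 94.5%) and 5.7 to 8.3% narrower at 16.5% (coverage 90.8 to 93.1%). With five-level integer scores, n = 600, correlations of 0.3 to 0.7 and 2,000 runs, the one-draw intervals were 1.3 to 1.9% narrower at 4% and 5.5 to 7.8% narrower at 16.5%, where Wilson coverage was 93.1 to 93.3%. Other runs at n = 600 gave coverage of 94.5 to 95.3% at 3.9%, and 92.5 to 94.5% at 18%.

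**The case against.** The strongest reply is that little is at stake. Full single imputation arises only in the lowest branch, where few values are affected, and the branch cannot be known before the data. The primary endpoints are AEs and SAEs. The non-responder and observed-case repeats in SAP 12.2.2 do not use this imputation. Gaps are also made less likely: the vIGA-AD windows in SAP 5.4 are contiguous from Day 15, an unscheduled or early-termination score in the window replaces a missed scheduled one, and Protocol 5.6 collects vIGA-AD at unscheduled visits made for safety. The planned interval also carries between-imputation variance from dropout, which the formulas above leave out, so the relative shortfall would be smaller. All of this stands, and it limits the size of the point. It does not make ordinary Rubin pooling valid for these sets.

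Three stronger readings are tempting, and the documents do not support them.

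- A reader might infer that the rule lets 14% of Cohort-Week 24 (2% × 7) or 18% of Cohort-Week 52 (2% × 9) be singly imputed at a visit. The share is computed over all subjects, so it sets no limit by cohort. Those figures also need every gap to fall at a single visit, which nothing in the documents suggests.
- A reader might infer that the parent visits are guaranteed complete. The SAP says only that no missing data are expected there. Completing the parent study through Week 4 does not ensure that its Week 1 and Week 2 scores exist, and those visits are part of the imputation model.
- A reader might infer that the main vIGA-AD intervals will be materially too narrow whatever the data. The shortfall depends on the branch and on how the gaps are spread.

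**Conclusion.** The rule is wrong as written, and the likely effect is small. In the one-dataset branch the intermittent values carry no imputation variance, so the CIs for visit-level vIGA-AD proportions are too narrow. With gaps spread over visits at the 2% limit, the interval is about 1 to 2.5% narrower than one from 25 independent draws, and coverage is about 94 to 95%. With every gap at one visit, the worst case, it is about 4 to 10% narrower over one-visit shares of 14 to 18% (16.5% in the assumed mix), and coverage is about 90 to 94% depending on the model and correlation. The 3- and 10-dataset branches have the same fault in milder form.

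These sizes rest on the 550/950 mix, gaps missing completely at random, R² of 0 to 0.5 and no dropout; none of these is a figure the documents give for this purpose. No hypothesis test or primary endpoint depends on the result.

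**What to change.** In step 1, draw at least 25 MCMC datasets to a monotone pattern. In step 2, run one PMM imputation within each. Pool the resulting 25 or more independent sets by Rubin's rule with the same Wilson interval, and delete the 2%/5% table. The accompanying text that places all 7 or 9 visits in the OLE study can go with it, since four of them are parent-study visits.

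The cost is two settings in PROC MI and a short SAP amendment. At 25 draws the number of completed datasets is the same as in the lowest branch (25) and smaller than in the others (75 or 250). It also removes a choice that depends on the data.

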6.2.2 Non-Responder Imputation

For the vIGA-AD secondary efficacy endpoints (refer to Sections 12.2), missing endpoint values will also be imputed as a non-responder i.e., not achieving the endpoint criteria.

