4 POPULATIONS FOR ANALYSIS

4.1 Full Analysis Population

The full analysis population is defined as all subjects who are enrolled in this study.

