5.5 Derived Variables

All questionnaire scores will be derived by Biostatistics in the ADaM datasets using the formulas defined below, even if calculated scores are present in the EDC database. All pre-calculated scores will be ignored for analysis.

- With the following exception, vIGA-AD Score of Clear (0) or Almost Clear (1) = vIGA-AD of ‘Clear’ (0) or ‘Almost Clear’ (1). The exception is that for subjects who discontinued early from study due to an AE or lack of efficacy, the subject will be considered as not having a vIGA-AD score of Clear (0) or Almost Clear (1) for all pre-specified analysis visits (refer to Section 5.4) for which the subject’s day of last dose falls within or is before the start of the analysis visit window.
- With the following exception, vIGA-AD Success = vIGA-AD of ‘Clear’ (0) or ‘Almost Clear’ (1) plus at least a 2-grade improvement from baseline. The exception is that for subjects who discontinued early from study due to an AE or lack of efficacy, the subject will be considered as not having a vIGA-AD success for all pre-specified analysis visits (refer to Section 5.4) for which the subject’s day of last dose falls within or is before the start of the analysis visit window. vIGA-AD Success will be derived for both the Primary and OLE baselines (refer to Section 5.2)
- Date of last contact = the latest of last study visit date, last dose date, end-of-study date and end-of-treatment date.
- Post-OLE Week 4 study duration (days): The duration can be represented as End Date – Start Date +1. The start date of the Post-OLE Week 4 interval will be the date of the OLE Week 4 visit or OLE Day 29 if the subject missed the OLE Week 4 visit. The end date will be the date of last contact. This endpoint will be calculated only for subjects who enter the post-OLE Week 4 study period.
- Duration (days) of the first BIW dosing will be calculated from the first BIW dosing to the start of the succeeding QD dosing interval. Subject’s last contact date will be used to censor

 Innovaderm Research	STATISTICAL ANALYSIS PLAN, Final Version 1.0
Protocol Number: ARQ-151-313	Sponsor: Arcutis Biotherapeutics, Inc.

this endpoint (time-to-event analysis) or as the end date of this duration (analyzed as a continuous endpoint) for subjects who do not revert to a QD dosing regimen after the first BIW dosing. This endpoint will be calculated only for subjects who enter the post-OLE Week 4 study period with at least one BIW dosing interval.

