12 EFFICACY ANALYSES

Unless otherwise indicated, missing efficacy data will not be imputed.

Efficacy endpoints will be summarized based on the full analysis set. For change and percent change efficacy endpoints relative to baseline, summaries will be performed relative to both Primary Baseline and OLE Baseline (refer to Section 5.2).

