12.2.2 Sensitivity Analyses

As sensitivity analyses to the imputation method used for the main analysis of the vIGA-AD endpoints (refer to Section 12.2.1), the main analysis of these endpoints will be repeated, but using the following imputation method:

- Non-responder imputation (refer to Section 6.2.2)
- Observed cases (i.e., no imputation)

No sensitivity analyses will be performed for the secondary efficacy endpoints based on WI-NRS and EASI total score.

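### The non-responder rule in SAP 6.2.2 has no cohort or data cut-off limit, so visits that a subject was never due to attend count as treatment failures

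*SAP*

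**What the plan says.** The non-responder rule in SAP 6.2.2 is a single sentence: for the vIGA-AD secondary endpoints, "missing endpoint values will also be imputed as a non-responder i.e., not achieving the endpoint criteria".

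The SAP does recognise that Weeks 36 and 52 do not apply to Cohort-Week 24, but only within the multiple-imputation (MI) method of 6.2.1:

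- The visit table marks those two visits "Cohort-Week 52 subjects only".
- Step 1 counts expected visits as "7 visits during the OLE study for Cohort-Week 24 subjects and 9 visits during the OLE study for the Cohort-Week 52 subjects".
- Step 3 says "For Cohort-Week 24 subjects, imputed OLE Week 36 and Week 52 analysis visit values will be set to missing".

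Section 12.2.2 defines the sensitivity analyses: "the main analysis of these endpoints will be repeated, but using the following imputation method". Non-responder imputation and observed cases are the two replacements. Section 12 adds that "Efficacy endpoints will be summarized based on the full analysis set", and under 4.1 "The full analysis population is defined as all subjects who are enrolled in this study". Appendix 1 makes everyone in the population, per treatment group, the default percentage denominator unless otherwise specified.

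For timing, Section 1 says the interim analyses use data up to a pre-specified cut-off. Section 6.3 runs every planned analysis at the interim. The optional second interim is the one tied to the ARQ-151-311/312 rollovers completing all their visits.

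Section 5.5 has a related rule for early discontinuations caused by inefficacy or by an AE. In those cases "the subject will be considered as not having a vIGA-AD score of Clear (0) or Almost Clear (1) for all pre-specified analysis visits"; the visits meant are those whose window contains or follows the last dose. It has no cohort limit either. The vIGA-AD success endpoint has a parallel rule.

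**The concern.** Non-responder imputation is meant to show how far the MI result depends on data that should have been collected but were not. A visit that was never scheduled, or had not come due by the cut-off, is not missing in that sense. Section 6.2.2 nevertheless attaches to any missing value, and missing is the word that MI step 3 uses for the Cohort-Week 24 values at Weeks 36 and 52.

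Two artefacts follow from a literal reading. In the ARQ-151-311/312 rollovers, response appears to collapse after Week 24 because one cohort has left by design. At the first interim, response is lowered at every visit that some ongoing subjects have not reached.

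The planned tables would not expose the first artefact. SAP 3.6 dropped the general by-cohort analysis, and 6.6 keeps cohort splits only for the duration, cumulative-time and percent-of-time endpoints. A reader comparing the non-responder table with the MI or observed-case table could take the gap for sensitivity to missing data.

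**Working it through.** **The plan's own figure.** The MI table lists four parent-study time points (OLE Weeks -4, -3, -2 and Day 1).
- Adding OLE Weeks 4, 12 and 24 gives 4 + 3 = 7.
- Adding Weeks 36 and 52 as well gives 4 + 5 = 9.

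Both match SAP 6.2.1, so the plan's own count of expected visits excludes Weeks 36 and 52 for Cohort-Week 24.

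**Inputs.**
- n24, the size of Cohort-Week 24: 275 + 275 = 550, an approximate planning figure from the protocol's Summary of Changes.
- n52, the number of Cohort-Week 52 subjects among the ARQ-151-311/312 rollovers: not stated, and no cap is documented. Assumed 200 to 950. The upper end is 1500 - 550 = 950, an extreme that leaves no ARQ-151-315 rollovers.
- p, the response rate that a correct non-responder analysis of Cohort-Week 52 would give: illustrated at 40%, 50% and 60%.

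**Cohort effect at Weeks 36 and 52.** Cohort-Week 24 adds n24 failures and no successes, so

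reported rate = p × n52 / (n52 + n24).

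| n52 | factor | p = 40% | p = 50% | p = 60% |
|---|---|---|---|---|
| 200 | 200/750 = 0.267 | 10.7% | 13.3% | 16.0% |
| 400 | 400/950 = 0.421 | 16.8% | 21.1% | 25.3% |
| 600 | 600/1150 = 0.522 | 20.9% | 26.1% | 31.3% |
| 950 | 950/1500 = 0.633 | 25.3% | 31.7% | 38.0% |

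If n24 were only 400, a correct 50% would be reported as 16.7% (200/600), 25.0% (400/800) or 35.2% (950/1350). The factors would differ for vIGA-AD success from OLE baseline, because 12.2.1 leaves out subjects already clear or almost clear at that baseline.

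**First interim.** If a share r of the subjects for whom a visit is scheduled has reached its due day, the rate is multiplied again by r. No cut-off date is given, so r is unknown. For illustration, p = 50% becomes:
- 0.5 × 0.9 = 45%
- 0.5 × 0.7 = 35%
- 0.5 × 0.5 = 25%

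Both effects can act together. At Week 36 or 52 with n52 = 400 and r = 0.5, the reported rate is 0.5 × 0.5 × 400/950 = 10.5%.

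**Section 5.5 rule in the MI and observed-case tables.** Assume 2% or 5% of 550 Cohort-Week 24 subjects stop for an AE or lack of efficacy and are scored as failures at Weeks 36 and 52. Take n52 = 400, all evaluable, and p = 50%.
- 2%: 0.02 × 550 = 11, and 200/411 = 48.7%.
- 5%: 0.05 × 550 = 27.5, and 200/427.5 = 46.8%.

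**With the limit in place.** The factor and r both become 1. With no truly missing data, the reported rate equals p.

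**The case against.** The strongest reply is that the cohort part is already settled by context. The SAP signals three times that Weeks 36 and 52 are outside Cohort-Week 24, and step 3 gives a design reason rather than one specific to MI. Section 12.2.2 repeats the main analysis and changes only the imputation. A careful programmer could carry the exception over, and the table layouts, kept in a separate document and not seen here, may do so. That reading is possible, but neither 6.2.2 nor 12.2.2 states it, and Section 1 says the SAP guides the analysis and deviations are not expected. It also cannot rescue the interim, because MI has no exception for visits not yet due.

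On 5.5, the reply is that step 3 expressly mentions subjects who discontinue before Week 24. That stands in part. However, step 3 clears imputed scores before the endpoints are derived, while 5.5 acts on the derived endpoint, so step 3 does not clearly block it. The effect is small in any case.

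The Appendix 1 denominator is only a formatting default and is weak support by itself. The size is uncertain: n52 = 200 has no basis in the text and the interim shares are illustrative. The consequence is limited too, since the primary endpoints are AEs and SAEs and the MI and observed-case tables appear alongside. If cohort shares are similar across prior-treatment groups, those groups are diluted alike. These points bear on weight, not on whether the gap exists.

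A practical objection is that due days built from visit windows fall before the SAP's wider analysis windows close. An ongoing subject at Day 100 could be scored a failure for Week 12 although data are accepted to Day 127. That is true. But the Week 52 analysis window never closes, and waiting for closure while keeping early observed values would bias rates upward.

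**Conclusion.** The concern holds on the wording. Section 6.2.2 scores unscheduled and not-yet-due visits as failures, and nothing in the SAP expressly prevents it.

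The cohort effect is confined to the ARQ-151-311/312 rollovers at Weeks 36 and 52. Under the assumed range it would cut the non-responder rate by more than a third even in the most favourable case (factor 0.633 at n24 = 550, n52 = 950). At n24 = 400 and n52 = 950 the factor is 0.704, a cut of about 30%. The direction is certain under a literal reading, but the exact size is not, because the cohort split is undocumented. The interim effect applies to the first interim analysis only, and its size depends on the cut-off date.

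No hypothesis tests are planned (SAP 5.7), and the rule serves a sensitivity analysis of two secondary endpoints. The damage is therefore to description: a spurious fall in response, and a table that no longer measures sensitivity to missing data. This should be corrected before the tables are produced, but it does not threaten the trial's primary conclusions.

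**What to change.** In 6.2.2 and in the 5.5 exceptions, add:

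> Non-response is assigned only at analysis visits scheduled for the subject's cohort. Cohort-Week 24 subjects are excluded from numerator and denominator at OLE Weeks 36 and 52.

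Placed in 5.5, this governs the MI, non-responder and observed-case tables alike.

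For the first interim, add to 6.2.1 and 6.2.2, and apply the same due rule to the 5.5 exceptions:

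> A missing value is imputed only if the visit was due by the data cut-off. Values observed before the due day are retained. The denominator is reported at each visit.

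Define due by calendar time from OLE Day 1, identically for ongoing and discontinued subjects. Otherwise discontinued subjects enter the denominator before comparable ongoing ones and pull the rate down. Target day (SAP Table 3) plus visit window (protocol 1.3) gives:

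- Week 4: 29 + 3 = Day 32
- Week 12: 85 + 7 = Day 92
- Week 24: 169 + 7 = Day 176
- Week 36: 253 + 7 = Day 260
- Week 52: 365 + 7 = Day 372

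In MI, values imputed at visits not yet due can be set back to missing afterwards, as step 3 already does for Cohort-Week 24.

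The cost is one sentence each in 5.5, 6.2.1 and 6.2.2 for the substance of these rules, and one flag for visit scheduled and due, derived from dates and cohort already held.
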